Finally, sinus floor augmentation represents an excellent model to study the behavior of bone repair based on bone substitutes, since a sample of the repaired bone can be taken at the time of implant installation, precisely in the same place where it will be placed. The relevance of this study is to show the importance of developing protocols that favor the prompt installation of dental implants after repair of the maxillary sinus floor augmentation with the objective that patients can be rehabilitated in a shorter time. Being the use of teriparatide, in local dose, mixed with a xenograft, an excellent possibility to improve both the quality of the repaired bone, as well

as to reduce the waiting time between the surgical steps and the prosthetic steps. Thus, a prompt oral rehabilitation can be guaranteed, improving the quality of stomatognathic health, and consequently improving the quality of life of patients.

EXPECTED RESULTS

The results of this study, once proven, may present the use of teriparatide as a protocol for the regeneration of critical bone defects not only in implantology, also be used in the reconstruction of defects associated with dentofacial anomalies, in the treatment of complications and bone sequelae related to trauma and oral and maxillofacial pathologies.

MATERIAL AND METHODS

This project corresponds to a randomized, triple-blind controlled clinical study that is part of the Doctoral Program in Dentistry, Concentration Area of Oral and Maxillofacial Surgery and Traumatology of the Fluminense Federal University - UFF (Niterói, Rio de Janeiro, Brazil) that will be carried out at the Department of Oral and Maxillofacial Surgery and Traumatology of the School of Dentistry of the University of Valparaíso in conjunction with the Biomedical Research Center of the School of Medicine of the Valparaíso University between the years 2022 and 2025.

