The universe of study are patients treated at the Dental Clinic of the Faculty of Dentistry of the University of Valparaíso, Chile, for rehabilitation with dental implants. Patients should be evaluated for rehabilitation by the Postgraduate Course in Oral and Maxillofacial Implantology in conjunction with surgical planning by the Postgraduate Course in Oral and Maxillofacial Surgery and Traumatology of the School of Dentistry of the University of Valparaíso. Within the inclusion criteria, participants must be between 25 and 70 years of age, requiring the installation of implants in the upper jaw and presents pneumatization of maxillary sinus of ≤ 5 mm in height (according to conebeam tomography baseline) and must sign the free and informed consent for participation in this study. Exclusion criteria are: residual edges smaller than 4 mm in height, uncontrolled systemic disease (ASA 3, 4, 5 and 6), presenting with osteoporosis or any disease of bone metabolism, having undergone radiotherapy, patients with cancer, any systemic condition that affects calcium absorption, kidney disease, having coagulation disorders, history of sinusitis, maxillary sinus pathology, heavy smoking (> 1 pack per day), drug or alcohol users, pregnancy, treatment with drugs that affect bone metabolism, treatment with immunosuppressants, allergies, uncontrolled periodontal pathology and tooth extractions in the last three months.

The sample was calculated using <https://www.sealedenvelope.com/power/continuous-superiority/>. The calculation was performed based on the results of previous studies, with a standard deviation of 5.62% for the first variable (amount of bone formed) and a difference of 6.5% between the test and control groups, obtaining an effect size of 0.98.⁶¹ Occupying this effect size with a margin of error of 0.05 and a confidence level of 90%, a sample size of 38 participants was obtained, 19 for the control group (CG) and 19 for the study group (GTP), respectively.

Projecting the withdrawal of participants add up to 2 more participants in each group, so each group will have 21 participants counting with 42 participants as a total sample.

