randomization and upload this information (participant identification and graft used) to a spreadsheet shared with one of the alternative researchers. For the TPG (study group) will be made the mixture of 20 μ g of teriparatide (Forteo®, Ely Lilly, France, Technofarma- Chile), 0.64ml of saline solution (Sodium chloride 0.9%, Baxter, Chile) with 1g of Bio-Oss® (Geistlich, Dentalmax, Santiago, Chile). In the CG (control group) will be made the mixture of 1gr of Bio-Oss® (Geistlich, Dentalmax, Santiago, Chile) with 0.72ml of saline solution (sodium chloride 0.9%, Baxter, Chile).

The volumes of saline needed to hydrate 1gr of Bio-Oss® of the study (TPG) and control (CG) groups, respectively, were calibrated in the laboratory of the Biomedical Research Center of the Faculty of Medicine of the University of Valparaíso by the principal investigator. In TPG a dose of Forteo ® is applied (20 μ g of teriparatide per dose of 80 μ l) to 1gr of Bio-Oss®. In order to obtain complete hydration of the graft, through a BioPette ™ (Plus Single-channel 20 – 200 μ l pipette (Labnet, Edison, NJ- USA) 80 μ l of saline solution (0.9% sodium chloride, Baxter, Chile) were applied until hydration of the graft was achieved, calculating a total of 640 μ l. For CG, which does not present teriparatida, occupying the same pipette, 720 μ l of saline solution (0.9% sodium chloride, Baxter, Chile) were used. It should be noted that the employee responsible for the randomization will be the same to perform the preparation of the grafts. For this procedure this employee will be calibrated by the principal investigator in the use of pipette and mixture of grafts.

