The implant stability coefficient (ISQ) will be evaluated by measuring the resonance frequency (Osstell ®, Göteborg, Sweden) and the insertion torque at the time of implant installation. The value of the implanted stability coefficient will be measured in two mutually perpendicular directions (distal/medial and palatine/bucal).

Statistical calculations will be performed in Prism (GraphPad Software). The parametric data obtained should be submitted to the normality test (Shapiro-Wilk test). Once the normality of the data is confirmed, the effect of the treatment will be determined by the paired t-test at 95%; Otherwise, the Mann-Whitney test should be used, considering alpha= 5%. The effect of time on the bone level in relation to baseline and the frequency of resonance will be evaluated by ANOVA or Kruskal-Walis test, depending on the normality of the data, also considering alpha= 5%. Data are expressed in terms of mean or median and 95% confidence interval.

REFERENCES

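### The treatment effect is to be tested with a paired t-test, but the two arms are different, unmatched participants

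*Protocol*

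**What the plan says.** The same rule appears twice in the Protocol: in the abstract (Material and Method) and in the last paragraph of MATERIAL AND METHODS. Data are first checked with Shapiro-Wilk. If normality is accepted, "the effect of the treatment will be determined by the paired t-test at 95" per cent; if it is not, "the Mann-Whitney test should be used" at the 5% level. The sentence that follows gives the effect of time, for bone level and resonance frequency, to ANOVA or Kruskal-Wallis.

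The design is described earlier in MATERIAL AND METHODS:

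- "This project corresponds to a randomized, triple-blind controlled clinical study".
- The sample-size paragraph arrives at "19 for the control group (CG) and 19 for the study group (GTP), respectively". Two more per group for withdrawals make 21 + 21 = 42.
- Randomisation takes place once the patient has entered the surgical centre. A staff member is to "upload this information (participant identification and graft used) to a spreadsheet", which is one graft per participant.
- The biopsy that yields the amount of bone formed is taken once, at implant placement.

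No split-mouth, crossover or matched-pair feature is described. Split-mouth occurs only in the titles of cited studies.

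**The concern.** A paired t-test analyses within-pair differences, so each control value must have a natural partner in the test group. Here it has none. To run the test, the analyst would have to set a control participant beside an unrelated test participant, in practice by position in the data table. Sorting by enrolment date, identifier or outcome would give different p-values and interval widths from identical data.

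The rule also contradicts itself. Mann-Whitney is for two independent samples, so a Shapiro-Wilk result would decide whether the trial is treated as paired or unpaired. A normality test cannot settle that; the design does.

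This is the only test given for the treatment effect, and so for the amount of bone formed, the variable on which the sample size rests. Following it literally makes significance arbitrary and open to choice after the data are seen. A withdrawal in one arm can also remove an unrelated participant from the other.

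**Working it through.** **Inputs (Protocol, sample-size paragraph).** SD 5.62 percentage points, difference 6.5, stated effect size 0.98, 0.05 and 90% (read as alpha and power), 19 per group, 21 with withdrawals. The quotient 6.5/5.62 is 1.16, not 0.98. That is a separate matter, so both values are carried below.

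**1. Which design reproduces the protocol's own sample size?**

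- Two independent groups, d = 0.98, one-sided 0.05, 90% power, t-based: 18.55, so 19 per group and 38 in total. This matches.
- Paired formula with standardised difference 0.98, two-sided 0.05, 90% power: 13.01, so 14 pairs. One-sided gives 10.43, so 11 pairs. Neither matches.

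The trial was sized as two independent groups.

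**2. Why row order matters.** With n per arm, the standard errors of the mean difference are

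- unpaired: √[(s₁² + s₂²)/n], on 2n − 2 degrees of freedom;
- paired: √[(s₁² + s₂² − 2·r·s₁·s₂)/n], on n − 1 degrees of freedom,

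where r is the sample correlation across rows. For unrelated people r is noise set by the ordering, with standard deviation about 1/√(n − 1) = 1/√18 = 0.236. Its middle 95% is therefore about ±0.46.

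With both SDs 5.62 and n = 19, √(2/19) = 0.3244, and the 95% half-widths are:

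| Analysis | Calculation | Half-width |
|---|---|---|
| Unpaired, 36 df | 2.028 × 5.62 × 0.3244 | 3.70 |
| Paired, r = 0, 18 df | 2.101 × 5.62 × 0.3244 | 3.83 |
| Paired, r = +0.46 | 3.83 × √0.54 | 2.81 |
| Paired, r = −0.46 | 3.83 × √1.46 | 4.63 |

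**3. One dataset, many orders.** Simulated arms of 19, observed SDs fixed at 5.62, observed difference 4.0, 20,000 random pairings:

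- Unpaired: p = 0.035, half-width 3.70.
- Paired: middle 95% of p-values 0.008 to 0.085, full range 0.00005 to 0.117; half-widths 1.60 to 5.10; p < 0.05 in 64% of orders.
- Both arms sorted in the same direction: p = 3 × 10⁻⁹. Sorted in opposite directions: p = 0.13.
- The mean difference is 4.0 every time.

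**4. Many datasets.** Independent normal arms, 19 per arm, 200 random row orders per dataset, two-sided 5%:

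| | d = 0.98 | d = 1.16 |
|---|---|---|
| Datasets where at least one order gives a different verdict from the others | about 30% | about 17% |
| Datasets where the middle 95% of p-values straddles 0.05 | about 23% | about 12% |
| Single random order agrees with the unpaired test | about 95% | about 97% |
| Median ratio, 97.5th to 2.5th percentile of p | about 27 | about 45 to 49 |

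**5. Power and type I error (noncentral t, two-sided 5%).** With no true correlation, the paired test has standardised difference d/√2.

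| | Unpaired | Paired |
|---|---|---|
| d = 0.98, 19 per arm | 83.6% | 81.5% |
| d = 0.98, 21 per arm | 87.3% | 85.5% |
| d = 1.16, 19 per arm | 93.4% | 92.1% |
| d = 1.16, 21 per arm | 95.5% | 94.5% |

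If rows are fixed at 21 and the two withdrawals per arm fall on four different rows, 21 − 4 = 17 pairs remain. Paired power at d = 0.98 is then 76.5%, against 83.6% for the unpaired test on the 19 + 19 completers. Simulated type I error of the paired test with arbitrary pairing is 4.98%.

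**The case against.** The strongest reply is that this is a slip for unpaired. The fallback test and the sample size both assume independent groups, so the intention is visible and a competent analyst may never run the paired version. That is probably right about intent. It does not remove the problem: the paired test is written in two places as the prespecified analysis. Following it is wrong, and departing from it without amendment is an undocumented deviation.

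The second reply concerns size, and most of it stands:

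- The point estimate is unaffected; only the p-value and interval width move.
- If row order is unrelated to outcome, type I error is about 5%, and power with complete rows falls by only 1 to 2 points.
- The 30% figure counts a dataset if any one of 200 orders disagrees, and it falls to about 17% at d = 1.16. One arbitrary order changes the verdict relative to the unpaired test in only about 3 to 5% of datasets.
- The 27-fold ratio of p-values overstates the practical harm, because much of it lies among values already well below 0.05.
- The 76% power figure is a worst case. It needs rows fixed before withdrawal and all four withdrawals on different rows.

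These limits describe average performance under a blind, fixed row order. They do not answer the objection that the result can be chosen by sorting.

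A within-person reading of paired does not help either. Time effects have their own test in the next sentence, and the amount of bone formed is measured only once.

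**Conclusion.** The concern holds. The stated test does not fit the stated design, and the two branches of the rule assume different designs. It must be corrected before analysis.

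The average cost is modest: 1 to 2 points of power with complete rows, up to about 7 points (83.6% to 76.5%) in the worst withdrawal pattern, and no long-run inflation of type I error if row order is unrelated to outcome. The serious part is that for a borderline result the verdict is arbitrary. In the example with unpaired p = 0.035, 64% of row orders reach significance and 36% do not.

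The figures assume independent normal arms with equal SDs, 19 completers per arm, two-sided 5% tests, and an effect of 0.98 or 1.16. The protocol names no primary outcome formally; the main comparison is taken to be the one on the amount of bone formed, which the sample size uses.

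**What to change.** In the abstract and in the last paragraph of MATERIAL AND METHODS, replace the paired t-test with an unpaired (Welch) two-sample t-test comparing the teriparatide group with the control group at two-sided alpha 5%, and report the mean difference with its 95% confidence interval. Keep Mann-Whitney as the rank-based counterpart.

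Only the word unpaired is needed to remove the defect. Welch is the usual safe choice when equal variances are not assured. The protocol does not state sidedness, and 19 per group at d = 0.98 with 90% power is reproduced only with a one-sided 0.05. Writing two-sided therefore makes explicit that power at d = 0.98 is about 84% with 19 per arm (about 87% with 21), and the sample-size paragraph should be worded to agree.

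The cost is a short amendment in two places. Data, software and number of participants are unchanged, and the result no longer depends on row order.

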For the beginning of the histological and histomorphometric analysis, the bone nuclei removed in the implant placement surgery should be fixed with 4% paraformaldehyde (PFA 4%) and stored at 4°C for 24 hours before the beginning of the laboratory procedures. These samples will be worked together with the collaborators of the Center for Biomedical Research, of the Laboratory of Morphological Analyses of the Faculty of Medicine of the University of Valparaíso.

All bone samples should be decalcified in 10% EDTA solution for 2 weeks at room temperature. Subsequently, these samples must be subjected to an ascending series of alcohol, starting 50, 70, 80, 95, 100, then Xylol. Then they should be soaked in paraffin blocks and these should be cut into serial sections 5 µm thick along the central axis of the biopsies, deparaffinized, rehydrated and stained with hematoxilin and eosin.^{23,24} Three sections of each sample should be randomly and blindly analyzed by an experienced pathologist who should perform descriptive histological analysis using a millimeter scale fitted to the 40x magnification eyepiece of a BH2 microscope (Olympus Optical Company, Ltd., Tokyo, Japan) for counting blood vessels, mesenchymal stromal cells, osteoblasts, osteoclasts, and osteocytes per mm². In addition, a histomorphometric analysis of separately quantified areas will be performed by means of a point system that should be stored in the ImageJ® SOFTWARE (NIH, USA, <http://rsb.info.nih.gov/ij>) in 10 random images captured at 10x magnification under a microscope with DP70 digital camera (Olympus) to study the following parameters: necrosis, inflammation, vascularization and angiogenesis, fibrosis, presence of medullary adipose tissue, bone neoformation and foreign body reaction. It is noteworthy that the collaborators who will work in the histological evaluation of the samples will be blind as to the attribution of the graft, because the samples donated by the participants will have a registration number that replaces the name of the participant (e.g. PARTICIPANT 1) in order to reduce the risk of bias, in addition to maintaining the anonymity

during the study. However, these antecedents are recorded in the database of the principal investigator, so it will be known to which sample each participant corresponds.

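### The outcome the trial is sized on is never named as primary, and an unadjusted 5% rule for the treatment effect is left open to some 8 to 19 outcomes

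*Protocol*

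**What the plan says.** **Sample size (Protocol, Material and Methods).** The calculation uses "a standard deviation of 5.62% for the first variable (amount of bone formed"), a between-group difference of 6.5% and a stated effect size of 0.98. It reaches 19 participants per group, raised to 21 for withdrawals.

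**Aims.** There is one general aim without an endpoint. Four specific aims follow, covering histological description, histomorphometry, bone volume on tomography and implant stability. None is ranked above the others.

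**Histology (Material and Methods).** A pathologist carries out an analysis called descriptive, "for counting blood vessels, mesenchymal stromal cells, osteoblasts, osteoclasts, and osteocytes per mm²". A separate histomorphometric analysis covers "necrosis, inflammation, vascularization and angiogenesis, fibrosis, presence of medullary adipose tissue, bone neoformation and foreign body reaction".

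**Other measurements.** Insertion torque is taken at implant placement. The abstract has resonance frequency (ISQ) at three times and tomographic bone level at four, three of them after grafting.

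**Statistics (last paragraph of Material and Methods).** If the data are normal, "the effect of the treatment will be determined by the paired t-test at 95"%. If not, "Otherwise, the Mann-Whitney test should be used, considering alpha= 5"%. The effect of time on bone level and resonance frequency is tested by ANOVA or Kruskal-Wallis, "depending on the normality of the data, also considering alpha= 5"%. The paragraph lists no outcomes for the treatment test, no hierarchy and no adjustment.

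**The concern.** A 5% test controls error for one comparison. The protocol's hypothesis, that the combination stimulates repair and improves bone morphology, could be addressed by several of the listed outcomes, and the text does not say which one decides it. The sample-size paragraph points to bone formation, but it gives neither a measurement method nor a time point, and the pointer goes no further.

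The choice of deciding outcome could therefore be made, or changed, after the data are seen. The trial would be sized for one question while a positive conclusion could be drawn from another, at an overall false-positive rate that the nominal 5% does not describe.

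**Working it through.** **1. The plan's own figure.** The inputs are effect size 0.98, alpha 0.05 and 90% power, taking the protocol's "a margin of error of 0.05 and a confidence level of 90"% to mean alpha and power. A one-sided 5% t-test needs 18.55 per group, rounded up to 19, so 38 in total is reproduced. The calculation has room for one outcome only and no allowance for several.

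**2. How many outcomes might be tested.** The statistics paragraph does not list them, so the count depends on the reading:
- Seven histomorphometric parameters plus insertion torque: 7 + 1 = 8.
- Adding ISQ at three times and bone level at three post-graft times: 8 + 3 + 3 = 14.
- Adding the five cell and vessel counts: 14 + 5 = 19.

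**3. Chance of at least one false positive, either direction.** For *k* independent tests at two-sided 5% (sidedness is not stated, so this is assumed), the chance is 1 − 0.95^k:
- *k* = 8: 1 − 0.95^8 = 0.337
- *k* = 14: 1 − 0.95^14 = 0.512
- *k* = 19: 1 − 0.95^19 = 0.623

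**4. Allowing for correlation.** The documents give no correlations, so a range is assumed. For normal test statistics with equal correlation ρ, condition on the shared component z. The chance is 1 − E[{Φ((1.96 − √ρ·z)/√(1−ρ)) − Φ((−1.96 − √ρ·z)/√(1−ρ))}^k], with z standard normal.

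| Tests | Independent | ρ = 0.5 | ρ = 0.7 |
|---|---|---|---|
| 8 | 34% | 25% | 19% |
| 14 | 51% | 35% | 25% |
| 19 | 62% | 41% | 28% |

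For 19 tests the figure drops below 50% at a common correlation of about 0.35.

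**5. Only false positives favouring teriparatide.** Under two-sided 5% testing each test contributes 2.5%:
- *k* = 8: 1 − 0.975^8 = 0.183
- *k* = 19: 1 − 0.975^19 = 0.382

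The benchmark for one primary outcome is 2.5% in this direction and 5% in either direction.

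**The case against.** The strongest reply is that the lead outcome can be identified. The sample-size paragraph calls the amount of bone formed the first variable and rests the whole calculation on it. It matches bone neoformation in the histomorphometry list, and the reference cited for its figures is titled a histological and histomorphometric study. This stands: the trial has an implicit lead outcome. But the reader has to infer it, and the plan also contains tomographic bone volume and bone level. The inference binds nobody at analysis.

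Second, a reader might infer that 19 outcomes are each tested at 5%. The protocol does not say so. It calls the cell-count work descriptive, and its aims separate describing histology from analysing histomorphometry. For bone level and ISQ it names a test of time, not a group comparison at each visit. The three ISQ times come from the abstract; the surgical section describes only placement and three months later. Nineteen is therefore an upper count and eight a fair lower one.

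Third, a reader might infer that a false positive is more likely than not. That needs about 14 or more tests that are independent or only weakly correlated. Twelve of the 19 outcomes come from the same bone core and six are repeats in the same patient, so correlation is to be expected. The 62% also counts errors in both directions and is not the risk of wrongly declaring benefit.

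Fourth, a reader might infer that any one significant result counts as proof. The protocol sets a testing rule and states no success criterion, so it does not say this.

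Finally, handling of secondary outcomes may sit in an analysis plan that is not shown. That is accepted. Naming the deciding outcome, however, belongs in the protocol.

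**Conclusion.** The point holds in this form: the variable the trial is sized on is not designated primary in the aims or the statistics, and the 5% rule for the treatment effect is neither adjusted nor limited to an outcome. With no true effect, the chance of at least one false positive in either direction is 34% to 62% for 8 to 19 independent tests, and about 19% to 28% at a correlation of 0.7. Favouring teriparatide only, it is 18% to 38% if independent. These figures assume two-sided 5% tests and, where correlated, a common correlation that the documents do not supply.

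Even the lowest two-direction figure, 19%, is nearly four times the nominal 5%. The documents do not show that a false positive is more likely than not, that all 19 outcomes are tested, or that any single result would be accepted as proof. This is a gap worth closing before analysis rather than a flaw in the design itself.

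**What to change.** In the aims and in the statistics paragraph, name the histomorphometric amount of newly formed bone in the biopsy taken 3 months after grafting as the single primary outcome, compared between groups at two-sided 5%. Label every other outcome secondary or exploratory, report each with an estimate and 95% confidence interval, and state that none of them can establish efficacy on its own.

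This takes about one paragraph and no extra participants or procedures. The downside is that a significant secondary result can no longer be claimed as confirmatory.

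One consequence should be checked in the same edit. At 90% power, 19 per group follows from 0.98 only with a one-sided 5% test. Two-sided, 19 per group gives about 84% power at 0.98, or about 93% at 6.5/5.62 = 1.157, the ratio the protocol's own inputs imply. The stated effect size and sidedness should be reconciled when the primary test is written down.

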Objectives: The aim of this study is to analyze the effect of a dose of teriparatide combined with a xenograft on maxillary sinus augmentation, to observe the microarchitecture of the neoformed bone and the primary and late stability of implants installed in these grafts. **Material and Method:** The sample, is composed of 42 participants who have clinical and radiological indication of subantral grafting for presenting residual bone height \leq 5 mm in the posterior maxillary region for the installation of dental implants. The sinus augmentation will be grafted with Bio-Oss® or Bio-Oss® combined with 1 dose (20 μ g) of teriparatide (Forteo®). Three months after grafting, at the time of installation of the dental implants, bone biopsies will be obtained using a short 2mm trephine drill. These bone nucleous will be fixed in 4% paraformaldehyde and will be submitted to histological and histomorphometric analysis. The stability of the implants will be measured, at the time of their installation, through the insertion torque, and through the use of resonance frequency equipment (Ostell®) in three moments: immediately and at 3 and 6 months after the installation of the dental implants. The bone level will be evaluated by cone beam tomography at four times: T0 (baseline), T1 (1 week after maxillary sinus enlargement), T2 (3 months after maxillary sinus enlargement and before implant insertion) and T3 (6 months after prosthetic connection). The parametric data obtained will be submitted to the normality test (Shapiro-Wilk test). Once the normality of the data found is confirmed, the effect of the treatment will be determined by the paired t-test at 95%. Otherwise, the Mann-Whitney test should be used, considering alpha=5%. The effect of time on the bone level in relation to baseline and the resonance frequency will be evaluated by ANOVA or Kruskal-Walis test, depending on the normality of the data, also considering alpha=5%. The data will be expressed in terms of mean or median and 95% confidence interval. The calculations will be performed in Prism (Graphpad Software).

Keywords: Teriparatide, Bio-Oss®, bone regeneration, bone substitutes, maxillary sinus floor enlargement, dental implants .

INTRODUCTION

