- To evaluate through cone beam tomography the maintenance of bone volume of mineralized lyophilized bovine bone graft combined with a local dose of teriparatide in sinus floor augmentation.
- To evaluate the stability of implants installed in grafted maxillary edges with the association of a single dose of teriparatide, associated with a mineralized lyophilized bovine bone graft.

JUSTIFICATIONS

Maxillary sinus augmentation is considered one of the most predictable and conventional procedures for the treatment of alveolar borders with insufficient bone volume and density. It is a procedure that aims to increase bone height through the placement of bone grafts/substitutes and consequently allows the installation of dental implants. It is also a procedure that should be performed in two stages (grafting and subsequent implant installation) in cases of severe atrophy (<5 mm residual height) with the aim of increasing the bone volume of the region to achieve primary stability at the time of installation of dental implants.

Along with this, several researchers have focused on studying the effectiveness of different bone substitutes to ensure optimal results both in the bone repair process and in the proper bone integration around dental implants, vital for the rehabilitation of edentulous patients. Teriparatide (PTH1-34) has been shown through several studies to have positive effects on bone regeneration through cellular mechanisms of proliferation and differentiation and thus improving trabecular bone formation.

In addition, it has been described that xenografts treated locally with teriparatide show clear evidence of increased cortical bone thickness, increased mineral apposition, and decreased amount of bone graft particles due to an increase in bone regeneration through the process of bone remodeling and replacement, in which bone graft particles are replaced by new bone¹⁹. We believe that the local mixture of teriparatide with xenograft accelerates bone mineralization in addition to increasing the hardness of regenerated bone, factors that directly influence the osseointegration of implants installed in these sectors.

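### For non-normal data the protocol tests the effect of time with Kruskal-Wallis, an independent-groups test, on measurements repeated in the same participants; the test is then too conservative and can lose power

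*Protocol*

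**What the plan says.** The closing statistical paragraph of Material and Methods says that the "effect of time on the bone level in relation to baseline and the frequency of resonance will be evaluated by ANOVA or Kruskal-Walis test", with the choice depending on normality and alpha set at 5%. The abstract repeats the rule: "the resonance frequency will be evaluated by ANOVA or Kruskal-Walis test".

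The abstract also fixes the measurement occasions. "The bone level will be evaluated by cone beam tomography at four times" (T0 to T3), and resonance frequency is measured "in three moments: immediately and at 3 and 6 months after the installation of the dental implants". The imaging paragraph of Material and Methods requires the scans in all selected participants. Both outcomes therefore form a series within each person.

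The comparison between treatments has its own tests, a t-test or Mann-Whitney. No Friedman test, mixed model or other within-participant method is named for time.

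**The concern.** Kruskal-Wallis ranks all values together and treats the visits as if they came from different people. The word ANOVA leaves room for a repeated-measures version; Kruskal-Wallis has no such version. Nor can the sentence mean a comparison of arms, because it speaks of the effect of time.

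Ignoring the pairing leaves the stable differences between participants in the noise. When a person's values are positively correlated over time, as is to be expected for the same site or implant, the real error rate drops below 5%, and a true change becomes harder to detect than with a matched rank test. Two specific aims depend on these series: implant stability, and the aim "To evaluate through cone beam tomography the maintenance of bone volume".

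This is not a detail left to a statistical analysis plan. The protocol names a specific test that does not fit its design.

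**Working it through.** **Inputs from the protocol.** Three ISQ occasions and four scan occasions (abstract); alpha 5%; 19 evaluable participants per group ("a sample size of 38 participants was obtained, 19 for the control group").

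**Assumptions, because the protocol gives no values.** Within-participant correlation ρ of 0.3, 0.5 or 0.7, equal between all visits; a linear change of 0.5 SD from first to last visit; normal data or one of two lognormal shapes. The protocol states no power for the time tests, so there is no figure of its own to reproduce.

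**The two statistics, n = 19 and k = 3.** In both, R_j is the rank sum at visit j, and the reference is chi-square on 2 df with 5% critical value 5.99.
- Kruskal-Wallis ranks all 19 × 3 = 57 values together: H = 12/(57 × 58) × Σ R_j²/19 − 3 × 58.
- Friedman ranks the three values within each participant: Q = 12/(19 × 3 × 4) × Σ R_j² − 3 × 19 × 4.

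**Why the size falls.** The difference between two visit means has variance 2σ²(1 − ρ)/n, but an independent-groups test allows for 2σ²/n. Under no change the statistic therefore shrinks by roughly (1 − ρ). On 2 df the chi-square tail is exp(−x/2), so the true size is roughly 0.05^(1/(1 − ρ)):
- ρ = 0.3: 0.05^1.43 = 1.4%
- ρ = 0.5: 0.05^2 = 0.25%
- ρ = 0.7: 0.05^3.33 = 0.005%

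Simulation across the distributions gives about 1-2%, 0.3-0.7% and under 0.1%. Friedman stays at about 5%.

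**Power of the whole rule.** Kruskal-Wallis is used only when normality fails, so the relevant comparison is the complete rule: Shapiro-Wilk at each visit, repeated-measures ANOVA if all visits pass, and otherwise either Kruskal-Wallis or Friedman. Power for 0.5 SD, n = 19, three visits:

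| Data | ρ | Kruskal-Wallis fallback | Friedman fallback | Loss (points) |
|---|---|---|---|---|
| Normal | 0.3 | 30% | 31% | 1 |
| Normal | 0.5 | 41% | 44% | 3 |
| Normal | 0.7 | 60% | 66% | 6 |
| Mild skew (log-SD 0.3) | 0.3 | 30% | 35% | 5 |
| Mild skew | 0.5 | 32% | 46% | 14 |
| Mild skew | 0.7 | 42% | 67% | 25 |
| Strong skew (log-SD 0.8) | 0.3 | 60% | 70% | 10 |
| Strong skew | 0.5 | 60% | 84% | 24 |
| Strong skew | 0.7 | 61% | 95% | 34 |

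Repeat runs move these figures by about 2 points. The fallback is reached in about 14% of normal data sets and in 97-99% of strongly skewed ones.

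The skewness of a lognormal is (e^(s²) + 2)√(e^(s²) − 1), and its coefficient of variation is √(e^(s²) − 1). At s = 0.3 these are about 0.95 and 31%; at s = 0.8, about 3.7 and 95%. The second shape is extreme for bone height or ISQ and serves as an upper bound.

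**Where little or nothing is lost.**
- Strong skew, change of 1 SD, n = 19: both tests reach 99% or more at every ρ.
- Two visits, strong skew, ρ = 0.3, n = 19, 0.5 SD: Kruskal-Wallis 72.6%, Wilcoxon signed-rank 67.9%.
- Both groups pooled (n = 38), normal data, 1 SD, ρ = 0.3: Kruskal-Wallis 98.5%, Friedman 97.6%.

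**Scans with T0 as a level of time.** Eligibility confines T0 height to 4-5 mm (at most 5 mm to enter; "Exclusion criteria are: residual edges smaller than 4 mm in height"). With an assumed graft gain of 3-5 mm and a later SD of 1-3 mm, Kruskal-Wallis rejects in 97-100% of trials if nothing is lost afterwards, and in 90-100% if half the gain is lost by T3. With an assumed jump of 7 SD, both tests reject in 100%.

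**Scans as gain over T0.** The conservatism remains. With T0 of the same spread as later scans and n = 21, Kruskal-Wallis size is 0.4-0.5% at every ρ from 0 to 0.7, because the gains share T0.

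**The case against.** The strongest reply is that the damage is small and rests on assumed figures. Much of this stands.

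- **Kruskal-Wallis is only a fallback.** Used on every normal data set, it would have 9% power against Friedman's 54% at ρ = 0.7, and a reader might quote that gap. The protocol does not support it, because normal data mostly go to ANOVA; the loss over the whole rule is then about 6 points. This takes the ANOVA to be repeated-measures, which the protocol does not say. An ordinary one-way ANOVA would have the same fault.
- **For bone level, the reading matters.** If T0 is a level of time, the graft step makes the overall test significant with either method and no power is lost. That such a test does not isolate maintenance after grafting applies equally to Friedman.
- **Friedman is not uniformly better.** At low correlation or with large changes Kruskal-Wallis can be slightly ahead.
- **A non-significant time test might be read as proof of stability.** A reader might infer this, but no section says results will be interpreted that way, and estimates with 95% confidence intervals are also to be reported.

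None of this makes Kruskal-Wallis a matched test. The named method does not fit the design, and it does not hold the stated 5% once visits are positively correlated.

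**Conclusion.** The point holds for the non-normal branch. With positive within-participant correlation, Kruskal-Wallis runs at about 1-2% down to under 0.1% instead of 5%. For a 0.5 SD change in 19 participants over three visits, the rule as a whole loses between about 1 point (normal data, ρ = 0.3) and 34 points (strong skew, ρ = 0.7). Mild skew, at 5 to 25 points, is the more plausible range. The correlation, size of change and shape of the data are all assumptions.

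Two stronger conclusions might be drawn and are not supported. The first is that the trial's main result is at risk: only secondary within-participant time tests are affected, not the randomised comparison or the bone-formation outcome that set the sample size. The second is that false positives are inflated: the error runs the other way under positive correlation. The one exception found is narrow, about 6% at zero correlation with a much smaller spread at T0 (SD 0.3 against 1), and the test is conservative again from ρ = 0.3.

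It is a clear error of modest consequence that is cheap to correct.

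**What to change.** In the abstract and in the statistical paragraph of Material and Methods, replace Kruskal-Wallis with the Friedman test, or with Wilcoxon signed-rank where an outcome has only two visits. State that the ANOVA is repeated-measures. This is a wording change that needs no new data, visits or participants.

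Separately, the number and timing of visits must be settled. The abstract and the imaging paragraph place T3 six months after prosthetic connection, while the implant-stage paragraph places it three months after implant installation. The abstract lists three ISQ measurements, while the implant-stage paragraph describes only two. Those passages must be reconciled, but the measurements are repeated in the same participants either way.
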